3.2.2 Key Secondary Outcomes

1. Amount of parenteral iron administered (in mg) during the 24-week treatment period in the pomalidomide and placebo groups (calculated as average mg/4-week interval to account for patients who discontinue early).
2. Amount of packed red blood cell transfusions (in units) during the 24-week treatment period in the pomalidomide and placebo groups (calculated as average units/4-week interval to account for patients who discontinue early).
3. Change in Neuro-QoL™ Satisfaction with Social Roles and Activities Short Form (V1.1) T-score from baseline (randomization visit) to weeks 12 and 24 (key timepoint), and the 4-week post-treatment follow-up visit in the pomalidomide and placebo groups.
4. Change in the HHT-specific QOL total score from baseline to weeks 12 and 24 (key timepoint), and the 4-week post-treatment follow-up visit in the pomalidomide and placebo groups.
5. Change in average daily epistaxis duration from the four-week screening period prior to baseline to weeks 8-12 and to weeks 20-24 (key timepoint), and to weeks 1-4 post-treatment in the pomalidomide and placebo groups.

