9 EFFICACY ANALYSES

9.1 Overview of Efficacy Analysis Methods

- All efficacy analyses will be performed on the mITT population, the primary population.
- All efficacy variables will be summarized by treatment group at baseline and at subsequent study time points at which assessments were administered and collected. Count (N), mean, standard deviation, minimum, and maximum will summarize continuous efficacy variables, whereas number and percent will summarize categorical efficacy variables.
- Unless otherwise noted, all analyses of dichotomous outcomes, measured at respective time points, will be performed using models as specified in Section 9.3. Efficacy models will be adjusted for stratification by clinical site. Baseline value will be an additional covariate for all analyses of change from baseline scores. Consistent with the description of the primary analysis in the protocol, analyses of primary and secondary outcomes will also include an independent variable for study visit. For analysis of measures assessed at multiple time points (for example, C1 and C6), longitudinal modeling will be used and the interaction between time and treatment groups will be included. Unless otherwise noted, all analyses of continuous efficacy variables (e.g., ESS and QOL scales) will be performed using general linear mixed models. Variables with distributions substantially different from normal will be transformed prior to analysis.

Models will be adjusted for pooled clinical site. If there are not enough patients per clinical site, similar sites will be combined (see Section 7.6)

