Variable	Type	Definition
Activities Short Form (V1.1) T-score at 12 and 24 weeks and 4 weeks post-treatment		is calculated as a T score using Neuro-QoL online scoring tools (https://www.assessmentcenter.net/ac_scoringservice), where a score of 50 represents the average of the Neuro-QoL calibration sample, which is a general US population, with a standard deviation of 10. The outcome will then be computed as the difference in score at each post-baseline visit and the score at baseline. Missing items within an assessment are handled by the official online scoring tools.
Change from baseline in HHT QoL Total Score at 12 and 24 weeks and 4 weeks post treatment	Continuous	The HHT QoL Total Score will be computed at baseline and at each study visit during which assessments are administered and collected by summing all of the items (Kasthuri et al 2022). The outcome will then be computed as the difference in score at each post-baseline visit and the score at baseline. If any data items at a time point for the assessment are missing, the outcome variable will be coded as missing.
Change from baseline in average daily epistaxis duration 8-12 and 20-24 weeks and 4-weeks post-treatment	Continuous	The average daily epistaxis duration will be computed at baseline and at each study visit during which the epistaxis diary is collected (See Appendix 2). The outcome will then be computed as the difference in average at each post-baseline visit and the average at baseline. If data at a time point for the assessment are missing, the outcome variable will be coded as missing. The daily average is calculated by averaging all non-missing data across all available days in a diary. At least 7 total days for each diary must be present in order to calculate the average for that time period. If the actual number of minutes for a nosebleed is not provided but the duration category is checked, then the midpoint of the duration category will be used as the duration for that nosebleed as follows: <1: 0.5, 1-5: 3, 6-15: 10.5, 16-30: 23, 31-60: 45, > 60: 60 Note: at masked data review, the unit of this outcome was modified from weekly to daily.
Other Secondary Outcomes		

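### Nosebleeds recorded only as over 60 minutes are set to 60 minutes, a value outside the category, so each is understated; the duration effect would probably be attenuated, by an unknown amount

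*SAP*

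**What the plan says.** The fifth key secondary outcome in SAP 3.2.2 is: "Change in average daily epistaxis duration from the four-week screening period prior to baseline to weeks 8-12 and to weeks 20-24 (key timepoint"), with a post-treatment comparison as well. It is one of the five endpoints tested by the Hochberg procedure in SAP 7.7.

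SAP 9.2 gives the derivation. On the daily value: "The daily average is calculated by averaging all non-missing data across all available days in a diary". A diary needs at least 7 days. On the change: "The outcome will then be computed as the difference in average at each post-baseline visit and the average at baseline".

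The fallback for incomplete entries is: "If the actual number of minutes for a nosebleed is not provided but the duration category is checked, then the midpoint of the duration category" stands in for the duration. The values are listed as "<1: 0.5, 1-5: 3, 6-15: 10.5", then "16-30: 23, 31-60: 45, > 60: 60". No reason is given for the last value. The rule is the same for both arms and all diary periods.

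SAP 7.3 states that no sensitivity analyses are planned for secondary analyses.

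**The concern.** The list is presented as the result of a midpoint rule, but its last entry cannot come from that rule. A bleed longer than 60 minutes cannot last 60 minutes, so the error always runs downward for the bleed concerned. Two consequences follow.

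- **Measurement depends on how the entry was made.** A 120-minute bleed counts as 120 if minutes were entered and as 60 if only the category was ticked.
- **The steps are uneven at the severe end.** Moving from the top category to the next is worth 60 - 45 = 15 minutes; the next step down is worth 45 - 23 = 22 minutes.

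The population has moderate to severe epistaxis, and long bleeds weigh heavily in a mean measured in minutes. The endpoint is formally tested. Under Hochberg, if the largest of the five p-values is not below 0.05, the next largest is held to 0.025, so a distorted result on one endpoint can change what is claimed for the others.

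**Working it through.** **1. Reproducing the listed values.** Midpoint = (lower + upper)/2, using the category limits in SAP 9.2.

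| Category (min) | Midpoint | SAP value |
|---|---|---|
| <1 | (0 + 1)/2 = 0.5 | 0.5 |
| 1-5 | (1 + 5)/2 = 3 | 3 |
| 6-15 | (6 + 15)/2 = 10.5 | 10.5 |
| 16-30 | (16 + 30)/2 = 23 | 23 |
| 31-60 | (31 + 60)/2 = 45.5 | 45 |
| over 60 | no upper limit, so none | 60 |

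Four values match exactly. The fifth is off by half a minute, which is trivial (45 fits if the limits are read as 30 and 60). No reading of the rule gives 60 for the last; 60 is the upper limit of the 31-60 category.

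**2. Understatement per affected bleed.** This is m - 60, where m is the true mean length. The documents give no m, so a range is assumed:

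- m = 75: 15 minutes (20% of the true length)
- m = 90: 30 minutes (33%)
- m = 120: 60 minutes (50%)

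**3. Effect on the tested arm difference.** Patients are randomised, and SAP 7.2 and 9.1 put the baseline value in the model. Understatement at baseline is then the same in both arms in expectation and largely cancels. What remains comes from follow-up. With nP and nD the category-only over-60 bleeds per patient on placebo and on drug, on the untransformed scale:

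loss in arm difference ≈ (nP - nD) × (m - 60) / diary days

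For each bleed by which nP exceeds nD over an assumed complete 28-day diary, the loss is 15/28 = 0.54, 30/28 = 1.07 or 60/28 = 2.14 min/day for m = 75, 90 or 120. With an assumed nP = 3 and nD = 1 it is twice that: 1.07, 2.14 or 4.29 min/day.

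**4. Cases with no effect or a reversed effect.**

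- nP = nD with equal lengths: the loss is zero.
- Recording differs by arm. Suppose both arms average two over-60 bleeds of 90 minutes, with minutes entered on placebo and only the category ticked on drug. Then nP = 0, nD = 2, and the formula gives -2 × 30/28 = -2.14 min/day, so the drug looks better than it is.
- Recording differs by period. Take one patient's over-60 bleeds only: four at baseline with minutes, two at follow-up without, all 90 minutes. The coded improvement is (4 × 90 - 2 × 60)/28 = 8.57 min/day; the true one is (4 × 90 - 2 × 90)/28 = 6.43.

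**5. Within-patient change, for scale only.** Assume that over 28 days over-60 bleeds, all category-only, fall from 4 to 1, and other bleeds of 10.5 minutes fall from 20 to 14.

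- Coded improvement: [(210 + 240) - (147 + 60)]/28 = 8.68 min/day.
- With m = 75: [(210 + 300) - (147 + 75)]/28 = 10.29; the coded value is 16% smaller.
- With m = 90: [(210 + 360) - (147 + 90)]/28 = 11.89; 27% smaller.
- With m = 120: [(210 + 480) - (147 + 120)]/28 = 15.11; 43% smaller.

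These percentages describe one assumed patient's improvement, not the arm difference that is tested.

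**The case against.** The best defence is that this is a fallback with little reach. It applies only when minutes are missing; participants were asked to record the duration of each event, and nothing in the SAP caps exact minutes above 60. The rule is identical across arms and was set before unmasking, so with no drug effect and similar recording it creates no arm difference. If the drug works, the lower limit is expected to be conservative. SAP 9.1 also says "Variables with distributions substantially different from normal will be transformed prior to analysis", which could reduce the leverage of the longest bleeds. Any larger substitute is itself a guess.

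Much of this stands. There is no evident threat to type I error, and the number of affected bleeds may be negligible. What does not stand is that 60 is a safe floor by design: the SAP calls it a midpoint, and the direction is not guaranteed (step 4). A transformation acts on values already cut to 60 and cannot restore the missing minutes.

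A reader might infer that most of the treatment benefit is lost. With one over-60 bleed a day at baseline and one 45-minute bleed a day at weeks 20-24, the coded change is -15 min/day against a true -30, -45 or -75 for m = 75, 90 or 120, so only 50%, 33% or 20% is kept. The documents do not support reading that as the effect on the trial result. It describes within-patient change, assumes that every bleed at baseline is category-only, and has no over-60 bleed at follow-up. If that held in both arms, the expected bias in the arm difference would be about zero.

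**Conclusion.** The value is wrong as written. SAP 9.2 states a midpoint rule and assigns a number that is neither a midpoint nor inside the category, so every category-only over-60 bleed in a formally tested endpoint is understated. The loss per bleed is 15, 30 or 60 minutes under assumed true lengths of 75, 90 or 120.

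The effect on the arm difference is probably attenuation. That rests on the drug reducing the number or length of such bleeds at follow-up and on similar recording habits in the two arms. Its size cannot be stated, because the documents do not say how many bleeds have only a category. With no sensitivity analysis planned for this endpoint, the report would not show whether the choice mattered. A flat statement that improvement is shrunk, or by how much, goes further than the documents allow.

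**What to change.** Before unmasking, amend SAP 9.2 and the derivation program:

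1. Replace 60 with the median of exact diary minutes recorded above 60, pooled over arms and periods. If there are too few such records, use a stated value inside the category, for example 90. State that the top category does not follow the midpoint rule.
2. Report the number of category-only over-60 bleeds by period, and by arm after unmasking.
3. Repeat the duration analysis with 60, 75 and 120 as a check.

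The cost is a few lines of text and code, using data already collected and keeping the blind. The downside is an assumption that bleeds with exact minutes resemble those without; the repeat analyses show how much rests on it. If the count proves negligible, item 2 settles the matter.

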In addition to epistaxis, AVMs involving the gastrointestinal (GI) tract, particularly the small bowel, are responsible for GI bleeding as the primary symptom in 15-20% of patients with HHT. HHT may also be associated with additional manifestations including brain abscesses and stroke resulting from cerebral AVMs and paradoxical right to left shunts through pulmonary AVMs. Patients may also develop liver AVMs which in extreme cases may cause high output congestive heart failure.

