#### **Other Secondary endpoints**

6. Change in PROMIS® Emotional Distress – Depression Short Form (V1.0) T-score from baseline (randomization visit) to weeks 12 and 24 (key timepoint), and the 4 week post-treatment follow-up visit in the pomalidomide and placebo groups.
7. Change in PROMIS® Fatigue Short Form (V1.0) T-score from baseline (randomization visit) to weeks 12 and 24 (key timepoint), and the 4 week post-treatment follow-up visit in the pomalidomide and placebo groups.
8. Proportion of patients requiring no red blood cell transfusion or parenteral iron infusion during the 24 week treatment period in the pomalidomide and placebo groups.
9. Change in the ESS from baseline to that recorded at each individual patient assessment, including the 4 week post-treatment follow-up visit.
10. Change in the ESS from baseline to the average of the week 16, 20 and 24 assessments.
11. Proportion of patients requiring endoscopic interventions for management of bleeding during the 24 week treatment period in the pomalidomide and placebo groups.
12. Incidence and severity of adverse events in the pomalidomide and placebo groups including but not limited to:
  - Venous thromboembolism
  - Arterial thromboembolism
  - Thrombocytopenia
  - Neutropenia
  - Peripheral neuropathy
  - Fatigue
  - Constipation/diarrhea
  - Rash
  - Any other AEs or SAEs of at least moderate severity that are possibly related to pomalidomide
13. Change in iron/hemoglobin-related studies including iron saturation, ferritin, hemoglobin, hematocrit, MCV, and MCHC.

---

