3.2.3 Other Secondary Outcomes

1. Change in PROMIS® Emotional Distress-Depression Short Form (V1.0) T-score from baseline (randomization visit) to weeks 12 and 24 (key timepoint), and the 4-week post-treatment follow-up visit in the pomalidomide and placebo groups.
2. Change in PROMIS® Fatigue Short Form (V1.0) T-score from baseline (randomization visit) to weeks 12 and 24 (key timepoint), and the 4-week post-treatment follow-up visit in the pomalidomide and placebo groups.
3. Proportion of patients requiring no red blood cell transfusion or parenteral iron infusion during the 24-week treatment period in the pomalidomide and placebo groups.
4. Change in the ESS from baseline to that recorded at each individual patient assessment, including the 4-week post-treatment follow-up visit.
5. Change in the ESS from baseline to the average of the week 16, 20 and 24 assessments.
6. Proportion of patients requiring endoscopic interventions for management of bleeding during the 24-week treatment period in the pomalidomide and placebo groups.
7. Incidence and severity of adverse events in the pomalidomide and placebo groups including but not limited to:
 - Venous thromboembolism
 - Arterial thromboembolism
 - Thrombocytopenia
 - Neutropenia
 - Peripheral neuropathy
 - Fatigue
 - Constipation/diarrhea
 - Rash

- Any other AEs or SAEs of at least moderate severity that are possibly related to pomalidomide and deemed medically relevant at masked data review.

8. Change in iron/hemoglobin-related studies including iron saturation, ferritin, hemoglobin, hematocrit, MCV, and MCHC.

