Proportion of patients requiring endoscopic intervention through 24 weeks	Dichotomous (Yes/No)	
The number of endoscopic interventions for management of bleeding will be counted throughout the 24-week treatment administration. The outcome is calculated as “Yes” if ≥ 1 endoscopic intervention and “No” if no endoscopic interventions.
 
Endoscopic interventions are recorded by the site on the concomitant medications form, can be either nasal or gastroenterological interventions. Identification of endoscopic interventions (such as nasal cauter) will be confirmed by medical review. These were identified prior to database lock and include endoscopy, cauter, and embolization.

Incidence and Severity of Specific adverse events	Discrete	The incidence rate and maximum severity of the following adverse events will be calculated: MedDRA terms identified in blinded data review noted for each.

Variable	Type	Definition
		
 • Venous thromboembolism 
 ◦ Portal vein thrombosis, Deep vein thrombosis • Arterial thromboembolism 
 ◦ None found • Thrombocytopenia 
 ◦ Thrombocytopenia • Neutropenia 
 ◦ Neutropenia ◦ also Leukopenia, and also a category of (Neutropenia or Leukopenia) • Peripheral neuropathy 
 ◦ Neuropathy peripheral, Peripheral sensory neuropathy • Fatigue 
 ◦ Fatigue • Constipation/diarrhea 
 ◦ Constipation, Diarrhoea, Nausea, Abdominal pain • Rash 
 ◦ Rash popular, Rash pruritic, Rash maculopapular, Rash, Rash erythematous, Urticaria, Pruritus, Palmar erythema • Any other AEs or SAEs of at least moderate severity that are possibly related to pomalidomide and deemed medically relevant at masked data review: 
 ◦ Pulmonary embolism ◦ Mouth ulceration ◦ Alanine aminotransferase increased ◦ Tremor ◦ Dyspnoea and exertional dyspnoea (only the cases that meet criteria of at least possibly and at least moderate) ◦ Tachycardia (only the cases that meet criteria of at least possibly and at least moderate) ◦ Muscle spasms (only the cases that meet criteria of at least possibly and at least moderate)

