Groups will be compared for the proportion of patients relapsed, requiring no blood or iron, and requiring endoscopic interventions and other yes/no categorical outcomes using logistic regression with adjustment for baseline assessment (ESS score, whether the patient had required a blood transfusion or required an total iron infusion amount of at least 250 mg in the 6 months before the baseline visit, and ESS score, respectively), and study site. If events are rare, exact logistic regression will be used.

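### SAP 9.2 counts embolization as an endoscopic intervention and lists endoscopy without its bleeding condition, so the counted set does not match the named secondary endpoint

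*SAP*

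**What the plan says.** Protocol section 4.2.2, item 11 among the other secondary endpoints, reads: "Proportion of patients requiring endoscopic interventions for management of bleeding during the 24 week treatment period in the pomalidomide and placebo groups". Protocol section 10.2 repeats it, and SAP section 3.2.3, item 6, uses the same words.

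The definition table in SAP section 9.2 turns this into a Yes/No variable:

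- Counting rule: "The number of endoscopic interventions for management of bleeding will be counted throughout the 24-week treatment administration". One or more scores Yes.
- Source and anatomical scope: "Endoscopic interventions are recorded by the site on the concomitant medications form, can be either nasal or gastroenterological interventions".
- Confirmation: "Identification of endoscopic interventions (such as nasal cauter) will be confirmed by medical review". No criteria for that review are given.
- Result of the identification: "These were identified prior to database lock and include endoscopy, cauter, and embolization". I read the third-last word as cautery.

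The analysis (Protocol 10.4.3, SAP 9.4) is logistic regression adjusted for baseline ESS and site, with this provision in the SAP: "If events are rare, exact logistic regression will be used". SAP section 7.7 places the endpoint outside the five key secondary outcomes, so it is not judged for significance. SAP section 12 reports that nothing was changed relative to the protocol.

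**The concern.** The endpoint name has two conditions: the procedure is endoscopic, and it is done to manage bleeding. The list of identified procedures strains both.

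Embolization fails the first condition, because it is done through a vascular catheter. Endoscopy meets the first, but it is listed with no statement that each one met the second. An endoscopy may be only a diagnostic look, and the text gives no rule for telling the two apart.

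What is at stake is the label on a result. A reader of the final report will take the proportion as patients who needed an endoscopic procedure for bleeding. If some are events only because of embolization, the proportion answers a wider question than the one named, and SAP section 12 would tell the reader that no such widening took place.

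**Working it through.** **Step 1: set the text side by side.** No figure in the documents can be reproduced here. Neither document gives an event rate, power or count for this endpoint. Protocol Table 9 covers a different binary endpoint, transfusion or iron infusion.

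| Element | Named endpoint (Protocol 4.2.2, SAP 3.2.3) | Identified set (SAP 9.2) | Match? |
|---|---|---|---|
| Cautery | Endoscopic intervention for bleeding | Listed | Yes, subject to review |
| Endoscopy | Only if an intervention for bleeding | Listed without that condition; review criteria not stated | Unclear |
| Embolization | Not endoscopic | Listed | No |
| Declared change | Not applicable | Section 12: none | Not disclosed |

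That embolization is not endoscopic is general medical knowledge; the documents do not define either term.

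**Step 2: how much one patient matters.** The site counts in SAP section 7.6 sum to 24 + 51 + 21 + 16 + 12 + 21 = 145. Assuming an exact 2:1 split, that is about 48 on placebo and 97 on pomalidomide. One reclassified patient moves the proportion by 1/48 = 2.1 points on placebo or 1/97 = 1.0 point on pomalidomide.

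**Step 3: illustration on assumed rates.** Let p be the proportion with a qualifying procedure and e the proportion with a non-qualifying one, equal in both arms and independent of p. The counted proportion is q = 1 − (1 − p)(1 − e). The unadjusted odds ratio is [q1/(1 − q1)] / [q0/(1 − q0)], with 1 for pomalidomide and 0 for placebo.

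For p0 = 20%, p1 = 10%, e = 5%: q0 = 1 − 0.80 × 0.95 = 24.0% and q1 = 1 − 0.90 × 0.95 = 14.5%. The odds ratio is (0.145/0.855)/(0.240/0.760) = 0.54.

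| Assumed placebo vs pomalidomide | e | Counted proportions | Odds ratio | Risk difference (points) |
|---|---|---|---|---|
| 20% vs 10% | 0 | 20.0% vs 10.0% | 0.44 | −10.0 |
| | 2% | 21.6% vs 11.8% | 0.49 | −9.8 |
| | 5% | 24.0% vs 14.5% | 0.54 | −9.5 |
| | 10% | 28.0% vs 19.0% | 0.60 | −9.0 |
| 30% vs 10% | 0 | 30.0% vs 10.0% | 0.26 | −20.0 |
| | 2% | 31.4% vs 11.8% | 0.29 | −19.6 |
| | 5% | 33.5% vs 14.5% | 0.34 | −19.0 |
| | 10% | 37.0% vs 19.0% | 0.40 | −18.0 |

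Under these assumptions the odds ratio moves toward 1 and the risk difference hardly changes. If the added procedures are embolizations for bleeding, treatment might reduce them too, and the equal-e assumption would not hold. The table shows sensitivity to the definition; it does not predict a result.

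**The case against.** The strongest reply is that the cell should be read as a whole. It restricts the count to nasal or gastroenterological procedures done for bleeding and has each identified procedure medically reviewed. The sentence with the list may only report which procedure types came up. Identification was done before database lock, and SAP section 4.4.2 keeps assignment masked until after lock, so no selection by arm is shown. The endpoint carries no significance test.

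Most of that stands, and it rules out several stronger readings:

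- **Embolization of lung or brain malformations is being counted.** Protocol section 2.1 does mention "stroke resulting from cerebral AVMs and paradoxical right to left shunts through pulmonary AVMs", but the cell's scope is nasal or gastroenterological and for bleeding. Read with those limits, such procedures are out.
- **Diagnostic endoscopies count.** The text does not say so. The counting rule excludes them if applied; the gap is that the list omits the condition and the review criterion is unstated.
- **Drug-related bowel symptoms add endoscopies on pomalidomide.** Constipation/diarrhea is a listed toxicity, but nothing links it to endoscopy or suggests such an endoscopy would pass review as bleeding management.
- **Pooling nasal and GI procedures is an error.** The protocol endpoint refers to bleeding, not epistaxis, and the ESS adjustment is in the protocol.
- **This is a rescue endpoint.** Protocol section 7.8 lists rescue procedures as not applicable.

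What the reply does not answer is embolization. No reading of the qualifiers makes it endoscopic, and section 12 does not disclose its inclusion.

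**Conclusion.** The mismatch is real and narrow. Embolization is in the set counted for an endpoint defined as endoscopic, and the SAP says nothing was changed. The entry for endoscopy is an ambiguity, because the list does not carry the bleeding condition that the counting rule requires.

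A reader might infer that the comparison is no longer of the named procedure at all. The documents do not support that: cautery, and endoscopy done for bleeding, remain in the set, and the number of embolization-only patients is not given.

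The size is unknown. The odds ratios above rest wholly on assumed rates, and even the direction depends on whether treatment also affects the added procedures. The consequence is limited to how one secondary endpoint, not tested for significance, is interpreted. SAP section 9.3.1 also refers to endoscopic interventions when discussing influences on the ESS, but it does not say that the section 9.2 list is reused there, so no effect on the primary analysis is claimed.

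**What to change.** Before unblinding:

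1. Compute the named endpoint without patients whose only procedure was embolization.
2. Count an endoscopy only where medical review confirms it was done to manage bleeding, and write that criterion into SAP section 9.2. No further condition, such as a treatment step during the endoscopy, is needed to match the protocol wording.
3. Report the broader set, any procedural intervention for bleeding including embolization, as a separately labelled supportive line. This keeps embolizations done to control bleeding in view.
4. Tabulate counts by procedure type and arm.
5. Record the difference from the protocol in SAP section 12.

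The cost is re-tabulating entries already under medical review, plus a few lines of SAP text. The downside is slightly fewer events for the named endpoint; the exact logistic regression already provided in SAP section 9.4 covers that.

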### 8.3 TIME PERIOD AND FREQUENCY FOR EVENT ASSESSMENT AND FOLLOW-UP

The occurrence of an AE or SAE may come to the attention of study personnel during study visits and interviews of a study participant presenting for medical care, or upon review by a study monitor. All AEs including local and systemic reactions will be captured on the appropriate CRF. Information to be collected includes event description, time of onset, clinician's assessment of severity, relationship to study product (assessed by the site PI or his/her designee), and time of resolution/stabilization of the event and any additional medical treatment employed in its management (assessed by the site PI or his/her designee). All AEs occurring while on study must be documented appropriately regardless of relationship. All AEs will be followed to adequate resolution.

Any medical condition that is present at the time that the participant is screened will be considered as baseline and not reported as an AE. However, if the study participant's condition deteriorates at any time during the study, it will be recorded as an AE. UPs will be recorded in the data collection system throughout the study.

If there are changes to severity of an AE during a single episode, the maximum severity experienced for that episode should be recorded. AEs characterized as intermittent require documentation of onset and duration of each episode.

The study site will record all adverse events with start dates occurring any time after informed consent is obtained until 7 (for non-serious AEs) or 30 days (for SAEs) after the last day of study drug. At each study visit, the investigator will inquire about the occurrence of AE/SAEs since the last visit. Events will be followed for outcome information until resolution or stabilization.

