10.2 Adverse Events

Per the protocol, participants were asked to report any adverse events from initiation of treatment through 24 weeks follow-up. All adverse events will be collected on an adverse event log and coded using MedDRA.

Adverse events will be listed and summarized by MedDRA system organ class and preferred term. Summaries will be of the number of events and number of individuals experiencing events by treatment group and will be created for all adverse events, by severity, and by relationship to treatment. Any events starting outside of the reportable time frame will be included in separate listings and will be excluded from summary tables. If a complete onset date is unknown and it cannot be confirmed that the event occurred during this time period, then the event will be considered a treatment-emergent adverse event.

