10.3 Deaths and Serious Adverse Events

A serious adverse event (SAE) is any event that is life threatening, results in death, causes or prolongs hospitalization, leads to a disability or birth defect, or requires an intervention to prevent a disability. SAEs will be listed, and SAEs and treatment-related SAEs will be summarized in the manner mentioned in Section 10.2 if there are enough events to summarize. Deaths will be listed.

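### SAP 9.2 counts venous thromboembolism without pulmonary embolism, and SAP 10.2 attributes to the protocol a 24-week adverse event window that conflicts with Protocol 8.3

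*SAP*

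**What the plan says.** **VTE terms.** Protocol 4.2.2 and SAP 3.2.3 share a safety outcome, "Incidence and severity of adverse events in the pomalidomide and placebo groups including but not limited to" a list whose first entry is venous thromboembolism. The definitions table in SAP 9.2 assigns MedDRA terms to each entry, chosen at blinded data review. For VTE the terms are "Portal vein thrombosis, Deep vein thrombosis". "Pulmonary embolism" stands further down, under the residual entry for other events of at least moderate severity that are possibly drug-related. For neutropenia the same cell adds "also Leukopenia, and also a category of (Neutropenia or Leukopenia"), which is a combined category. No combined category is given for thromboembolic events.

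**Window.** SAP 10.2 states: "Per the protocol, participants were asked to report any adverse events from initiation of treatment through 24 weeks follow-up". It goes on: "Any events starting outside of the reportable time frame will be included in separate listings and will be excluded from summary tables". SAP 10.3 adds that "SAEs and treatment-related SAEs will be summarized in the manner mentioned in Section 10.2 if there are enough events to summarize". Protocol 8.3 has sites record events starting "any time after informed consent is obtained until 7 (for non-serious AEs) or 30 days (for SAEs) after the last day of study drug". Both schedules of events (Protocol 7.3.7, SAP 4.5) collect adverse events at the week 28 visit. SAP 12 declares no departure from the protocol.

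**The concern.** Safety and tolerability is the first secondary objective. Thromboembolism is among the known risks in Protocol 2.3.1, and Protocol 8.1 classes every venous or arterial thromboembolism as a serious adverse event (SAE). A reader of the results will take the VTE row as the number of patients who had a VTE. With the SAP 9.2 terms it is not that number, and separate rows cannot be added to obtain it, because one patient may appear in both.

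The window sentence misreports the protocol. It is also the only time frame that SAP 10.2 states before excluding events outside the reportable frame from the summary tables. If it is used as written, SAEs that the protocol requires sites to record in the 30 days after treatment could appear in listings but not in the incidence tables by arm.

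**Working it through.** **1. VTE count.** The plan gives no figure to reproduce. Inputs: planned arms of 106 and 53 (Protocol 10.5, SAP 6); terms from SAP 9.2.

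- Weight of one patient whose only VTE was a pulmonary embolism: 1/106 = 0.9 percentage points on pomalidomide; 1/53 = 1.9 on placebo.
- If *a* patients are in the VTE row and *b* in the pulmonary embolism row, the number with any VTE lies between max(*a*, *b*) and *a* + *b*. For illustration only, with assumed counts *a* = 2 and *b* = 2 among 106, the VTE row shows 2/106 = 1.9%, while the any-VTE rate could be anything from 1.9% to 4/106 = 3.8%.

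**2. Window, side by side.**

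| | SAP 10.2 | Protocol 8.3 |
|---|---|---|
| Start | treatment initiation | informed consent |
| End, non-serious | 24 weeks | last dose + 7 days |
| End, serious | 24 weeks (if SAP 10.3 inherits it) | last dose + 30 days |

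Take 24 weeks as counted from first dose: 24 × 7 = 168 days, the same as six 28-day cycles.

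*Completer with no gaps (last dose day 168):*
- SAE period ends on day 168 + 30 = 198; outside the 24 weeks: 30/198 = 15%.
- Non-serious period ends on day 168 + 7 = 175; outside: 7/175 = 4%.
- If 24 weeks means the C6 visit, scheduled 0 to 5 days after week 24, the tails shrink to between 25 and 30 days (25/198 = 13% to 15%) and between 2 and 7 days (2/175 = 1% to 4%). The 15% and 4% are therefore upper figures for this patient.

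*Early stopper (last dose day 56, end of cycle 2):*
- Non-serious: the protocol end is day 56 + 7 = 63; the 24-week window ends 168 − 63 = 105 days later.
- SAE: the protocol end is day 56 + 30 = 86; the 24-week window ends 168 − 86 = 82 days later.
- The direction changes at a last dose on day 168 − 7 = 161 (non-serious) or 168 − 30 = 138 (SAE). Before those days the SAP window is the longer one.

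These are shares of days, not of events.

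**The case against.** **No pulmonary embolism is lost.** This stands. SAP 9.2 calculates incidence and maximum severity for each listed event, and pulmonary embolism is listed without the case-level restriction attached to dyspnoea, tachycardia and muscle spasms. It would also appear in the preferred-term tables and, if serious, in the SAE listing. A reader might infer that the plan hides pulmonary embolism; the text does not support that. What is missing is the patient-level total.

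**The total may exist in the table shells.** SAP 14 keeps these in a separate document, which was not available here. SAP 10.1 also names thromboembolism for group comparison without repeating the 9.2 terms. So the gap is established for the SAP text, not for every planned display. But SAP 9.2 is the only place where terms are assigned, and it assigns two.

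**The reportable time frame may mean Protocol 8.3.** This is a fair reading, because the 24-week sentence is descriptive and defers to the protocol. On that reading no event within the protocol's window drops out. The false attribution remains, though, and SAP 10.2 offers no other frame. A reader might infer that late SAEs will certainly be left out of the tables. The documents do not show this: it requires that the 24 weeks is the operative window and that SAP 10.3 inherits it.

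**A longer tail is tempting.** Protocol 6.1.5 lets each later cycle start within 5 days of the previous one, so a reader might add five delays and arrive at a larger untabulated share. The schedules place C6 at week 24 plus 0 to 5 days, which fits badly with a drift of that size. No such figure is claimed.

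**The effect is not one-sided.** This stands. SAP 5 identifies two participants who stopped drug for adverse events and had efficacy assessments for months afterwards. Under the Protocol 8.3 end points, any late non-serious events recorded for them would leave the main tables.

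**Conclusion.** Both textual defects hold and should be fixed. They concern safety reporting only.

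The VTE item as defined omits any patient whose only event was a pulmonary embolism, at 0.9 (pomalidomide) or 1.9 (placebo) percentage points per patient at the planned arm sizes. How many patients this affects is unknown. Because the terms came from blinded review and the arterial entry records none found, a reader might infer that at least one pulmonary embolism occurred. That is plausible, but the documents give neither a count nor an arm. That pulmonary embolism is a venous thromboembolic event is ordinary clinical usage; the documents do not say so.

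The window in SAP 10.2 contradicts Protocol 8.3 at both start and end. Its effect is conditional: up to 15% of SAE days and up to 4% of non-serious days untabulated for a gap-free completer, with the reverse for early stoppers. The phrase used in SAP 10.2 could also mean 24 weeks after treatment; that would not match Protocol 8.3 either. Excluded events would still be listed.

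A reader might also infer an effect on stopping or on the main result. There is none. The eight-event halting rule has its own, broader definition (Protocol 8.5, SAP 7.4.1). The primary endpoint, alpha and power do not use these data. SAP 7.7 attaches no significance claim to the other secondary outcomes.

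**What to change.** 1. In SAP 9.2, add pulmonary embolism to the VTE terms, or add an any-VTE row that counts each patient once across pulmonary embolism, deep vein thrombosis and portal vein thrombosis. Keep the separate lines.
2. In SAP 10.2 and 10.3, replace the 24-week sentence with the Protocol 8.3 end points: 7 days after last dose for non-serious events, 30 days for SAEs. State that the summary tables are treatment-emergent, starting at first dose, and that events between consent and first dose are listed separately. The later start is a deliberate choice and should be declared, since Protocol 8.3 begins at consent.
3. List, or tabulate separately, events recorded after those end points, including those in participants followed after stopping drug early.

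The cost is two SAP edits and a re-run of the adverse event and SAE tables on data already collected. If only an any-VTE display row is added, SAP 14 allows it without an amendment, provided it does not contradict the SAP text. Reported counts may move in either direction.
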